| Name of Study Drug | LX9211 phosphate |
| Protocol Number | LX9211.1-202-PHN LX9211.202 (Abbreviated number) |
| Protocol Title | A Phase 2, Double-blind, Randomized, Placebo-controlled, Parallel-group Study to Evaluate the Efficacy and Safety of LX9211 in the Treatment of Postherpetic Neuralgia (RELIEF-PHN1) |
| Primary Objective | To evaluate the efficacy of LX9211 in reducing pain related to postherpetic neuralgia (PHN) |
| Primary Efficacy Endpoint | The change from Baseline (Week 2 of the Run-in Period) to Week 6 in Average Daily Pain Score (ADPS), based on Question 5 of the Zoster Brief Pain Inventory (ZBPI), the 11-point numerical rating scale (0 [No Pain] to 10 [Pain as bad as you can imagine]) |
| Secondary Objectives | To assess other effects and patient reported outcomes of LX9211 versus placebo during and following the Week 6 double-blind Treatment Period |
| Secondary Efficacy Endpoints | 
 • Change from Baseline to Week 6 in pain interfering with sleep based on Question 9F of the ZBPI “Indicate the one number that describes how, in the past 24-hours shingles pain has interfered with your: Sleep (0 [Does not interfere] to 10 [Completely interferes])” • Proportion of patients with $\geq 30\%$ reduction in pain intensity in ADPS based on Question 5 of the ZBPI from Baseline to Week 6 • Proportion of patients with $\geq 50\%$ reduction in pain intensity in ADPS based on Question 5 of ZBPI from Baseline to Week 6 • Change from Baseline to Week 6 in interference in General Activity, Mood, Walking Ability, Normal Work (includes both outside the home and housework), Relations with other people, Sleep, and Enjoyment of Life interference based on the Questions 9A-G of the ZBPI • Proportion of patients discontinuing treatment due to lack of efficacy defined as increase in ADPS from Baseline of $\geq 30\%$ based on Question 5 of the ZBPI • Patient Global Impression of Change (PGIC) at Week 6 • Time to loss of efficacy from Week 6 to Week 11 among patients achieving $\geq 30\%$ reduction in pain intensity in ADPS based on Question 5 of the ZBPI. |

| | |
|---|---|
| Other Efficacy Endpoints | 
 • Change from Baseline to Week 6 in the Neuropathic Pain Symptom Inventory (NPSI) • Change from Baseline to each week in ADPS, based on Question 5 of the ZBPI • Proportion of patients with $\geq 30\%$ reduction from Baseline in ADPS, based on Question 5 of the ZBPI by week • Proportion of patients with $\geq 50\%$ reduction from Baseline in ADPS, based on Question 5 of the ZBPI by week • Cumulative distribution function of percent change in ADPS based on Question 5 of the ZBPI from Baseline to Week 6 comparing the LX9211 treatment group to placebo • Cumulative distribution function of percent change in ADPS based on Question 5 of the ZBPI from Week 6 to Week 11 comparing the LX9211 treatment group to placebo |
| Pharmacokinetic (PK) / Pharmacodynamic (PD) Objectives | 
To evaluate plasma levels of LX9211 in patients with PHN
 
Blood samples will be collected from patients [REDACTED]
 
[REDACTED]
 |
| Safety Objectives | 
Safety will be assessed by adverse events (AEs), vital signs, electrocardiogram (ECG) findings, and laboratory parameters
 |
| Phase of Development | 
Phase 2
 |
| Methodology | 
This is a Phase 2, multicenter, randomized, double-blind, placebo-controlled, parallel-group study in patients with PHN.
 
Scheduled study visits in the clinic will occur during Screening; at the initiation of the 2-week single-blind placebo Run-in Period; on Day 1 (Baseline); during Weeks 2, 4, and 6 of the double-blind Treatment Period; and Week 11 of the single-blind Safety Follow-up Period.
 
Male or female patients ≥ 18 years of age and older with prior herpes zoster skin rash and PHN pain persisting for ≥ 3 months after healing of the herpes zoster skin rash who meet all inclusion and no exclusion criteria are eligible for enrollment.
 
Eligible patients may continue use of 1 medication prescribed for PHN including pregabalin, gabapentin, and tricyclic antidepressant (TCA) medications as long as they have been at stable doses for ≥ 1 month prior to Screening. Patients who are taking more than 1 permitted concomitant medication for the treatment of PHN and are unable to washout of all but 1 of these treatments for the duration of the study are not eligible. Use of any new medications, prescribed or over the counter (OTC), for treatment of PHN pain is
 |

| | |
|--|---|
| | 
not permitted during the course of the study. Use of any opioid medications for the management of PHN within the 2 months prior to Screening is not permitted. Note: Brief use (<1 week) of opioid medication for management of non-PHN acute pain (eg, tooth extraction/acute injury) ≥ 2 months prior to Screening Visit is permitted.
 
Screening Period: After signing the Informed Consent Form (ICF), all patients will enter a Screening Period of up to 2 weeks. Patients using non-opioid medications that are prohibited by the protocol must discontinue or washout of these medications for ≥ 2 weeks prior to entering the Screening period. Following confirmation of eligibility criteria, patients will enter the following study periods:
 
Run-in Period: After meeting Screening eligibility criteria, patients will enter a 2-week single-blind Run-in Period in order to qualify that the criteria for moderate to severe pain are met and to demonstrate $\geq 80\%$ compliance with taking the expected amount of placebo tablets. On Day 1 of the Run-in Period patients will be dispensed 4 tablets of single-blind placebo to be administered at the site. For the remainder of the Run-in Period, patients will take a single tablet of study drug every morning. Each evening patients will rate and record intensity of their PHN pain based on Question 5 of the ZBPI by answering the question “Please rate your pain by indicating the one number that best describes your pain on the average in the last 24 hours”, on the 11-point numerical rating scale (0 [No Pain] to 10 [Pain as bad as you can imagine]). The ADPS will be calculated using all available daily pain diary data. The mean value of the ADPS derived over Week 2 will serve as the Baseline measure used for analyses. In order to qualify for randomization, patients must have completed $\geq 70\%$ of the daily pain diary entries during the second week of the Run-in Phase, meet criteria for moderate to severe pain and demonstrate $\geq 80\%$ compliance with taking the expected amount of placebo tablets during the Run-in Period. During the Run-in Period patients will not be allowed use of any rescue medication. On the morning of the Run-in Visit, patients may eat a light meal prior to the visit.
 
Note: Patients who fail Screening due to laboratory values may have those assessments repeated and be rescreened once after discussion with the Sponsor’s Medical Monitor.
 
Randomization/Double-blind Treatment Period: Patients who successfully complete the 2-week single-blind placebo Run-in Period and meet all other eligibility criteria will enter a 6-week double-blind Treatment Period.
 |
|--|---|

| | |
|--|--|
| | 
Patients will be randomly assigned in a 1:1 ratio between the following 2 treatment groups:
 
 • Group 1: LX9211 200 mg* / 20 mg**, once daily (qd) • Group 2: Placebo, qd matching loading and maintenance doses 
* Loading dose (Day 1)
 
** Maintenance dose (Day 2 – Week 6 Visit)
 
Implementation of the treatment randomization schedule will be centralized. A 1:1 ratio for assigning patients between the treatment groups will be accomplished by use of randomly permuted blocks of fixed size.
 
On Day 1, patients will receive LX9211 or placebo, to be given as a loading dose at the clinic. The loading dose will be followed by a daily maintenance dose taken at home on Day 2 through end of Week 6. Note: On days of clinic visits, patients will refrain from taking their daily dose until after the visit.
 
Each evening during the double-blind Treatment Period, patients will be required to rate and record the average severity of their PHN pain over the previous 24 hours using Question 5 of the ZBPI, record the use of rescue medication (acetaminophen), and rate the interference with sleep using the ZBPI Question 9F. The ADPS will be calculated using all available data; however, a minimum of 4 days (consecutive or nonconsecutive) from the last week prior to each clinic visit is required for the calculation.
 
If a patient is unable to tolerate their PHN, they are encouraged to discuss treatment options with the Investigator. At the Investigator's discretion, the patient may be permitted to take acetaminophen (up to a maximum of 3 grams per day) as a rescue medication. Only the acetaminophen provided by the Sponsor as a rescue medicine may be used during the course of the study. The use of personally acquired acetaminophen is prohibited. If rescue medication does not provide adequate pain relief, the patient may discontinue from further participation in the study after consultation with the Investigator. Patients who discontinue prior to completion of the Week 6 Visit will not be replaced.
 
Safety Follow-up Period: Following the double-blind Treatment Period, all patients will enter a 5-week single-blind Safety Follow-up Period. During this period, patients will dose with 1 tablet of single-blind study drug (placebo) every morning, taken at home. Patients will remain blinded to the study drug being taken. Each evening patients will continue to rate and record the average severity of their PHN over the previous 24 hours using the
 |

| Number of Patients | 
The proposed sample size is 74 patients, 37 randomized to each treatment group. The sample size will be reassessed at a planned interim analysis. The interim analysis will occur when the first 38 patients have been accrued and followed to endpoint at Week 6. Based on this assessment, the sample size will be reestimated and can remain as originally proposed or increased. The maximum increase is limited to 148 patients.
 
The interim analysis will allow for statistical testing of futility and should the prespecified futility boundary be crossed, and other data support a negative trial finding, consideration will be made to stop patient accrual.
 
Approximately 30 patients will be recruited to participate in a qualitative patient interview substudy for English speaking patients in the United States (US) only.
 | | |
| Study Population | 
Male and female patients 18 years or older will be enrolled. Patients will have a diagnosis of postherpetic neuralgia defined as pain in the dermatomal distribution of an acute herpes zoster skin rash, persisting for ≥3 months from the healing of herpes zoster
 | | |

| | | |
|--|--|---|
| | skin rash. Patients will have to meet pain criteria at the end of the Run-in Period. | |
| Number of Study Sites | Approximately 30 with the majority of sites located in the US and approximately 10 sites will be located in Europe | |
| Treatments | Each patient will be randomized to 1 of the following groups: | |
| Treatment Group | Loading Dose (Day 1) * | Maintenance Dose (Day 2 to Week 6 / EOT/EW) ** |
| Group 1: LX9211 200 mg*/20 mg** | 2 x 50-mg LX9211 tablets + 2 x 50-mg LX9211 tablets | 1 x 20-mg LX9211 tablet, qd |
| Group 2: Placebo | 2 x Placebo tablets + 2 x Placebo tablets | 1 x Placebo tablet, qd |
| * Loading Dose (Day 1) | | |
| ** Maintenance Dose (Day 2 – Week 6 Visit) | | |
| Route of Administration | Oral | |
| Duration of Treatment | Patients will be treated with double-blind study drug for 6 weeks. Patient participation will be approximately 105 days, including a 2-week Screening Period, a 2-week single-blind Placebo Run-in Period, a 6-week double-blind Treatment Period, and a 5-week single-blind Safety Follow-up Period. | |
| Inclusion Criteria | 
Patients must meet all of the following criteria to be considered eligible to participate in the study. For patients not meeting eligibility requirements, the reason for exclusion must be recorded. Note: Patients who are not eligible because of laboratory result(s) may have the laboratory test(s) repeated once during the Screening Period, at the discretion of the Investigator, to determine eligibility:
 
 1. Patient has given written informed consent to participate in the study in accordance with local regulations | |

| | |
|---------------------------|---|
| | 
 2. Adult male or female patients ≥ 18 years of age at the Screening Visit: 
 a. Females of childbearing potential must have a negative serum or urine pregnancy test prior to the start of study drug. In the case of positive urine pregnancy testing, a negative serum sample for pregnancy testing, to confirm that the patient is not pregnant, must be obtained prior to start of study. They must also agree to use adequate methods of contraception which include the following: condom with spermicidal gel, diaphragm with spermicidal gel, coil (intrauterine device), surgical sterilization, vasectomy, oral contraceptive pill, depo-progesterone injections, progesterone implant (ie, Implanon®), NuvaRing®, Ortho Evra® b. Nonsterile male patients with sexual partners of childbearing potential must agree to use adequate methods of contraception from Baseline through the Week 11 Visit 3. Presence of PHN pain that is present for ≥ 3 months after healing of herpes zoster skin rash affecting a single dermatome. Patients with more than 1 involved dermatome may also be included, provided the affected dermatomes are contiguous. 4. Moderate to severe pain as confirmed by average pain score using scores recorded in the pain diary in the 14 days prior to randomization (Run-in Period) 5. At least 80% compliance with dosing during the 2-week Run-in Period, and 70% compliance with completion of the daily diary during the second week of the Run-in Period 6. Willing to adhere to the prohibitions and restrictions specified in the protocol |
| Exclusion Criteria | 
Patients who meet any of the following criteria will be excluded from participating in the study:
 
 1. Presence of other painful conditions that may confound assessment or self-evaluation of PHN: 
 a. Patient should not have any other neurological disorder or conditions that can cause symptoms that may mimic peripheral neuropathy or that might confound assessment of PHN pain. |

| | |
|--|---|
| | 
b. Other causes of diffuse painful peripheral neuropathy such as: paraproteinemia, untreated hypothyroidism (previously treated hypothyroidism not excluded if treated and euthyroid for ≥ 6 months), vitamin B12 deficiency, neurologically-evident vasculitis, malignancy, amyloidosis, renal insufficiency, connective tissue disease (eg, Sjogren's, systemic lupus erythematosus), porphyria, complex regional pain syndrome, chronic inflammatory demyelinating polyradiculoneuropathy, alcoholism, HIV, hepatitis, uremia, syphilis, myeloma, or other systemic disease associated with a secondary painful neuropathy should be excluded.
 
c. Patient should not have had any exposure to drugs/toxic environmental agents known to cause neuropathy
 
2. Over the past year, met Diagnostic and Statistical Manual of Mental Disorders, 5th edition (DSM-5) criteria for a major depressive episode, any active, significant psychiatric disorders (eg, neurocognitive disorder, anxiety disorder, psychosis, bipolar disorder), or a history of clinically significant drug or alcohol use disorder that would, in the Investigator's opinion, interfere with the assessment and evaluation of pain during the study
 
3. Mood and anxiety disorder scores defined by Hospital Anxiety and Depression Scale (HADS) ≥ 13
 
4. Suspected or likely diagnosis of trigeminal neuralgia
 
5. Use of opioid medications for management of PHN within the 2 months prior to the Screening Visit. Note: Brief use (<1 week) of opioid medication for management of non-PHN acute pain (eg, tooth extraction/acute injury) ≥ 2 months prior to the Screening Visit is permitted.
 
6. Use of NSAIDs for the specific treatment of PHN pain.
 
7. Use of more than 1 permitted concomitant medications for the treatment of PHN. Note: Patients may washout additional PHN medications ≥ 1 month prior to the Screening Visit to reach the 1 permitted medication
 
8. For non-opioid medications patient uses and is unwilling/unable to discontinue use of prohibited medications and therapies, (eg, benzodiazepines, dextromethorphan, herbal medications, mexiletine HCl, adenosine, topical analgesics including lidocaine and
 |
|--|---|

| | |
|--|--|
| | 
capsaicin), applied to the same area of the body affected by PHN pain, nerve blocks, acupuncture, or other medications indicated for neuropathic pain. A patient using any of these interventions for neuropathic pain must discontinue the medication ≥ 1 month prior to starting the Screening Period and for the duration of the study. Note: This exclusion criterion does not include analgesics that are not specifically prescribed for treatment of neuropathic pain (eg, nonsteroidal anti-inflammatory drugs [NSAIDs], aspirin, acetaminophen). In addition, patients who are prescribed antidepressants for a mental health disorder are eligible to participate as long as they do not meet Exclusion Criteria 2-3.
 
9. A positive urine drug test for drugs of abuse including cannabinoids. Note: Cannabidiol (CBD), if used for mood or sleep, is acceptable. If used for PHN it would be allowed if it is the only concomitant medication being taken for PHN. If not the only medication being taken for PHN, it should be withdrawn ≥ 1 month prior to Screening
 
10. Patient has hepatic impairment at Screening, defined as any of the following: aspartate aminotransferase (AST) $> 2X$ upper limit of the normal reference range (ULN), alanine aminotransferase (ALT) $> 2X$ ULN, serum total bilirubin (TB) $> 2X$ ULN. Note: If it is the opinion of the Investigator and the Medical Monitor that an increase in bilirubin is due to Gilbert's syndrome, then the patient may participate.
 
11. Patient has abnormal kidney function test (estimated glomerular filtration rate [eGFR] < 60 mL/min as calculated using the Cockcroft-Gault equation) at Screening or renal dysfunction requiring hemodialysis
 
12. Patient has any of the following medical conditions or disorders: epilepsy or seizure disorder requiring treatment with antiepileptic drugs
 
13. Presence of clinically significant physical examination (PE) findings other than PHN, or laboratory or ECG findings that in the opinion of the Investigator, Medical Monitor, and/or the Sponsor, may interfere with any aspect of study conduct or interpretation of results including:
 
 any clinically significant abnormal heart rate or rhythm other ECG abnormalities that are clinically relevant |
|--|--|

| | |
|--|--|
| | 
c. BP >160/100 mm Hg or <90/50 mm Hg
 
d. presence of risk factors for torsade de points (eg, family history of long QT syndrome; personal history of NYHA class III/IV heart failure or structural heart disease)
 
14. Receipt of any investigational agent within 30 days or 5 half-lives, whichever is longer, prior to Baseline/Randomization on Day 1
 
15. Receipt of any therapeutic protein, antibody/biologic- or antibody-based agents (eg, growth hormones or monoclonal antibodies) within 3 months prior to dosing on planned Day 1. Note: Preventative vaccines (eg, influenza, pneumococcal, Tdap), will be allowed if administered >7 days prior to dosing. Patients who have previously received the shingles vaccine, but subsequently develop PHN and meet all inclusion and exclusion criteria, are eligible to participate.
 
16. Prior exposure to LX9211
 
17. History of any serious adverse reaction or hypersensitivity to any inactive component of study drug, unless the reaction is deemed irrelevant to the study by the Investigator, Medical Monitor, and/or the Sponsor
 
18. Presence of any skin condition, such as ulcers, which could interfere with assessment of PHN
 
19. Existence of any postsurgical or medical condition that, in the judgment of the Investigator, Medical Monitor, and/or the Sponsor, might interfere with the absorption, distribution, metabolism, or excretion of LX9211, including bariatric surgery, cholecystectomy, or any other GI surgery, except appendectomy and hernia repair, which are acceptable
 
20. History of any major surgery within 3 months prior to Baseline or surgery that is anticipated to be performed during the study period
 
21. History of any active infection within 30 days prior to Baseline, if deemed clinically significant by the Investigator, Medical Monitor, and/or the Sponsor
 
22. Malignancy or active treatment for malignancy (ie, radiation or chemotherapy, including monoclonal antibodies) within 5 years prior to the Screening Visit. Note: Patients with squamous or basal cell carcinomas of the skin, carcinomas in situ of the cervix or uterus, ductal
 |
|--|--|

| | |
|----------------------------|--|
| | 
breast cancer in situ, resected low-grade prostate cancer, or other malignancies that, in the opinion of the Investigator and the Medical Monitor are considered cured, may participate.
 
23. Donation or loss of >500 mL of blood or blood product within 3 months prior to Baseline
 
24. Inability or difficulty swallowing whole tablets
 
25. Any other condition that compromises the ability of the patient to provide informed consent or to comply with the objectives and procedures of this protocol, as judged by the Investigator, Medical Monitor, and/or the Sponsor
 
26. Unable or unwilling to adhere to the requirements of the protocol, or communicate or cooperate with the Investigator and/or their staff for any reason
 
27. Patient refuses to participate in processes if established by the Sponsor, to minimize duplicate patients (Verified Clinical Trials)
 
28. Employees, or relatives of the Sponsor, Investigator or study center staff, with direct involvement in the proposed study or other studies under the discretion of the Investigator or study center
 
29. Patient is immunocompromised (eg, secondary to transplant or require active immunosuppressive drugs)
 |
| Statistical Methods | 
A proposed sample size of 74 randomized patients will yield 82.27% power to detect a true mean difference of -0.68 units between the LX9211 treatment group and placebo in the primary efficacy endpoint, assuming a common standard deviation of 1 unit and a 2-sided significance level of $\alpha=0.05$. This derivation is adjusted for a uniform dropout rate of 15%, that patients will be randomly assigned to treatment in a 1:1 ratio, and for an interim analysis conducted after about half of the originally proposed sample size has been accrued and followed to endpoint. The sample size can be increased to a maximum of 148 patients based on a reestimation procedure performed at the planned interim analysis.
 
Continuous variables will be summarized by the mean, standard deviation, median, minimum, and maximum values for all patients with non-missing data. Categorical variables will be summarized by their counts and associated percentages. All data will be provided in individual patient listings.
 |

| | |
|--|--|
| | 
Analysis of the primary and secondary efficacy endpoints will be based on the Modified Intent-to-Treat (mITT) Population, defined as all randomized patients who had taken ≥ 1 dose of study drug. Safety endpoints analyses will be based on the Safety Population, defined as those patients who received any exposure to study drug.
 
A restricted maximum likelihood-based, mixed-effects model repeated measures (MMRM) approach will be used to assess the difference between LX9211 and placebo for the primary endpoint. The MMRM model will include fixed effects of treatment, week, treatment-by-week interaction, the randomization factor of Baseline pain severity, and Baseline score as covariate. An unstructured covariance structure will be used to model the within-patient error. The Kenward-Roger approximation will be used to estimate the denominator degrees of freedom. Other covariance structures will be explored should convergence not be met. In the event that a rescue medication is used, a supplementary MMRM model will be applied on a dataset that excludes data collected after the initiation of the rescue medication. To assess the robustness of the MMRM analyses performed under the missing at random (MAR) assumption, and given the long half-life of LX9211, pattern mixture models (PMM) with copy reference-based multiple imputation methods will be applied to both datasets (with and without data collected after the initiation of the rescue medication). The imputed datasets will be combined by use of Rubin's rule and analyzed using an analysis of covariance (ANCOVA) model fitted for the fixed effects of treatment, the randomization factor of Baseline pain severity and the continuous fixed covariate of Baseline score.
 
The number and percentage of patients who need rescue medication and/or prematurely dropout of the study will be summarized descriptively.
 
For the continuous, secondary and other efficacy endpoints: ZBPI score, PGIC score, and NPSI score, measured at multiple time points, a similar modeling strategy used for the primary endpoint will be applied. The proportion of responders based on Question 5 of the ZBPI, the 11-point scale (0 [no pain] to 10 [pain as bad as you can imagine]) will be compared between treatments using a Cochran-Mantel-Haenszel test stratified by the randomization factor of Baseline pain severity. A non-responder imputation (NRI) rule will be applied for all analyses based on categorical variables to assign outcomes to missing observations.
 
The qualitative patient interview substudy will be managed by a vendor (RTI-Health Solutions, Research Triangle Park, NC); data
 |
|--|--|

| | |
|-----------------------------|---|
| | analysis methods will be detailed in a separate statistical analysis plan and will be reported separately. |
| PK/PD Assessments | 
Blood samples for the determination of plasma LX9211 trough levels (C_{trough}) will be drawn predose on Day 1 and at Weeks 2, 4, 6, and 11. Blood samples will be drawn 2 hours after dosing on Day 1 for the determination of plasma 2-hour levels (C_{p2hr}).
 
[REDACTED]
 |
| PK/PD Analysis | 
C_{p2hr} and C_{trough} values will be summarized by treatment group, at each time point, using descriptive statistics.
 
[REDACTED]
 |
| Safety Assessments | Safety and tolerability of LX9211 will be assessed by collection and review of AEs, clinical laboratory results, ECG findings, and vital signs. |
| Safety Data Analysis | 
Safety analyses, based on the Safety Population, will involve examination of the descriptive statistics and individual patient listings for any effects of study treatment on clinical tolerability and safety. Summaries will be prepared by treatment group (ie, placebo and LX9211) and, by study visit where applicable. The incidence of AEs will be presented by severity and by relatedness as assessed by the Investigator. All safety data will be provided as listings.
 
Treatment-emergent adverse event (TEAE) summaries will include the overall incidence of TEAEs, incidence of TEAEs (by System Organ Class [SOC] and Preferred Term [PT]), TEAEs by maximum intensity, TEAEs by relationship to study treatment, events leading to discontinuation of study drug, deaths, and SAEs.
 
Vital signs, ECGs findings, PE findings, clinically significant PE findings, weight, and laboratory parameters (chemistry, hematology, and urinalysis) will be summarized descriptively at each time point. Actual and change from Baseline data will be calculated and summarized. In addition, shift table analyses will be presented for the laboratory data.
 |

Table of Contents

| | | |
|-------|---|----|
| 1. | Synopsis | 3 |
| 2. | List of Abbreviations and Definitions of Terms | 22 |
| 3. | Introduction..... | 25 |
| 3.1 | Background on LX9211 and Neuropathic Pain..... | 25 |
| 3.2 | LX9211 Nonclinical Pharmacology, Pharmacodynamics and Toxicology..... | 26 |
| 3.2.1 | In Vitro Pharmacodynamic Studies | 26 |
| 3.2.2 | In Vivo Pharmacodynamic Studies..... | 26 |
| 3.2.3 | Safety Pharmacology | 27 |
| 3.2.4 | Summary of Pharmacology | 27 |

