10.1 Determination of Sample Size

Proposed Sample Size

The proposed sample size is derived by satisfying the original design assumptions made for the primary efficacy endpoint. It is assumed that the difference in treatment group means is 0 under the null hypothesis (H_0) and is unequal to 0 under the alternative hypothesis (H_1); a 2-sided hypothesis under test. Under the H_1 , the difference in group means of LX9211 minus placebo is expected to be -0.8 units with a common standard deviation of 1.0 units. These assumptions yield an effect size of 0.8. The effect size is the absolute value of the difference in treatment group means divided by the common standard deviation of that difference. A uniform dropout rate of 0.15 is anticipated, and adjustment of the effect size for this rate results in an estimate 0.68; the adjusted difference in group means is equal to -0.8 units \times 0.85 = -0.68. For a 2-sided test sized at $\alpha = 0.05$, 37 patients per treatment group are required under a 1:1 randomization ratio to detect the stated treatment difference under H_1 with statistical power equal to 82.27% under a single stage design. The total planned $N = 74$ patients.

This study is designed as a group sequential trial with 1 interim look at approximately the 50% information time and a final analysis at 100%. A non-binding futility boundary will be used to test for futility of the primary endpoint. The futility boundary is 1-sided with $\alpha = 0.025$ and for the parameters specified, a power estimate of 82.53% is derived.

Sample Size Reestimation

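### The synopsis misstates the basis of its 82.27% power: −0.68 is the assumed −0.8 already diluted for dropout, and the figure is single stage, not interim-adjusted

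*Protocol*

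**What the plan says.** **Protocol synopsis, Statistical Methods.** "A proposed sample size of 74 randomized patients will yield 82.27% power to detect a true mean difference of -0.68 units", with SD 1 and two-sided α = 0.05. On dropout it says "This derivation is adjusted for a uniform dropout rate of 15" percent. It says the derivation is also adjusted "for an interim analysis conducted after about half of the originally proposed sample size has been accrued and followed to endpoint". The value −0.8 does not appear there. The paragraph closes by allowing an increase to 148 patients.

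**Protocol 10.1, repeated in SAP 2.3.** The difference under the alternative is "expected to be -0.8 units with a common standard deviation of 1.0 units". Dropout then enters by shrinking the effect: "adjustment of the effect size for this rate results in an estimate 0.68", that is 0.8 × 0.85. With 37 per arm this gives "statistical power equal to 82.27% under a single stage design". The next paragraph introduces one interim look with a non-binding futility boundary, for which "a power estimate of 82.53% is derived". That second figure is also the upper limit of the promising zone and the conditional power targeted by the reestimation.

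**Protocol 10.4.5.7 and SAP 7.8.** The interim is at 38 of 74 patients (51.4% information). Beta is spent by a power family with parameter 3.672, giving cumulative beta of 0.015 and 0.175. The SAP puts the futility bound at Z = −0.085.

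**The concern.** The synopsis and the body attach the same 82.27% to different statements. In the body, −0.68 is a diluted value standing in for a true −0.8, and no interim is involved. In the synopsis, −0.68 is the true effect, with dropout and the interim allowed for as well. At 74 patients both cannot be right.

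Many readers take the power statement from the synopsis. They would conclude that 74 patients give about 82% power for a real effect of 0.68 points after 15% dropout. Power at effects below −0.8 is a question the design itself raises, since Protocol 3.6 justifies reestimation by the wish to detect a smaller effect that still matters.

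A second, smaller issue is that the power quoted with a futility look (82.53%) exceeds the power quoted without one (82.27%). On a single basis, a non-binding futility look cannot do that.

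**Working it through.** **Inputs.** SD 1, two-sided α = 0.05, 37 per arm, differences −0.8 and −0.68, dropout 15% (synopsis; Protocol 10.1; SAP 2.3). Interim at 38/74 with futility bound −0.085 (Protocol 10.4.5.7; SAP 7.8).

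**1. Reproduce the stated figure.** Two-sample t-test, noncentrality = d × √(n/2), df = 2n − 2.
- d = 0.68, n = 37: noncentrality 0.68 × √18.5 = 2.925, df 72, power **82.27%**, an exact match.
- The normal approximation gives 83.27%.

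So the stated figure has all 74 patients evaluable, no loss of N and no interim.

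**2. Take the synopsis literally: true −0.68, 15% of patients lost, N fixed at 74.**
- Evaluable per arm: 37 × 0.85 = 31.45.
- Noncentrality 0.68 × √15.725 = 2.697; power 75.6% (t) or 76.9% (normal).
- With whole numbers, 31 per arm gives 75.0% and 32 per arm gives 76.4% (t).
- Applying the futility bound: 76.7% (normal).

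**3. Set both true differences against both ways of handling dropout (t-test).**

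| True difference | Effect × 0.85, 37 per arm (Protocol 10.1 method) | Full effect, 31.45 per arm |
|---|---|---|
| −0.8 | 82.27% (effect 0.68) | 87.7% |
| −0.68 | 68.9% (effect 0.578) | 75.6% |

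The 82.27% belongs to a true difference of −0.8. Neither method gives it for a true difference of −0.68. The right-hand column is closer to the planned primary analysis, an MMRM on observed data.

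**4. Allow for reestimation.** The documents do not fix every detail of the rule, so one was assumed: conditional power under the observed trend, increase if it lies between 50% and 82.53%, target 82.53%, cap 148, normal scale, futility bound obeyed. In 400,000 simulated trials with true −0.68 and 15% lost, power was 79.2%, against 76.7% on the same scale without reestimation. With true −0.8 and 15% lost it was 90.1%.

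**5. Effect of the futility look on one basis** (effect 0.68, 37 per arm).
- Interim information 38/74 = 0.5135; mean interim Z = 2.925 × √0.5135 = 2.096.
- Chance of stopping under the alternative: Φ(−0.085 − 2.096) = 0.0146.
- Normal: 83.27% falls to 83.09%. t-test (100,000 simulated trials): 82.25% falls to 82.10%.

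Neither basis yields 82.53%.

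**6. Check 82.53% against the beta spending.** 1 − 0.8253 = 0.1747, which rounds to the stated final beta of 0.175. At the interim, 0.1747 × (38/74)^3.672 = 0.0151, matching the stated 0.015. The figure is therefore consistent with the boundary specification. What is missing is the basis on which it was computed.

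**The case against.** The strongest reply is that this is loose wording in a synopsis. Protocol 10.1 and SAP 2.3 set out the derivation openly and agree with each other, and no sample size, boundary or analysis depends on the synopsis sentence. On the body's account, taking a further 15% off N after using −0.68 counts dropout twice, so 75–76% is not the power of the planned design. It also holds N at 74 when the design can grow to 148, and it gives dropouts no weight although the MMRM uses their earlier weekly scores. All of that stands. It confines the point to what the synopsis literally asserts and rules out calling 76% the design's power. It does not rescue the sentence: a true −0.68 with dropout additionally allowed for does not give 82.27%, and 10.1 labels the figure single stage.

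On 82.53%, the reply is that the gap is only 0.26 points (82.53 − 82.27), that the two figures carry different design labels, and that the t and normal bases themselves differ by a full point. This also stands. A reader might infer that 82.53% is an error and should be replaced wherever it is used, including in the promising zone. The documents do not support that: it agrees with the stated beta spending, and the evidence shows only that its basis is unstated.

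**Conclusion.** The synopsis misstates the basis of its power figure in two respects: it presents a dropout-diluted difference as the true one, and it describes a single-stage figure as interim-adjusted. Read literally, with true −0.68, 15% of patients lost, dropouts contributing nothing and N fixed at 74, power is 75.0–76.4%, about 6 to 7 points below the claim. With reestimation under the assumed rule it is about 79%, about 3 points below. MMRM may recover some of the loss.

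A reader might infer that the trial is underpowered. That does not follow. Under the plan's own assumption of −0.8 with 15% lost, power is about 88% at N = 74, so 82.27% is on the cautious side for that assumption.

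The two quoted powers, 82.27% and 82.53%, do not share a stated basis. The discrepancy is small; it is a matter of documentation and gives no ground for altering the adaptive rule.

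**What to change.** **Synopsis, Statistical Methods.** Reword along these lines: *true difference −0.8, SD 1, diluted to −0.68 for 15% dropout; 74 patients give 82.27% power in a single-stage design (two-sided α = 0.05)*. Delete the statement that this figure is adjusted for the interim. Optionally add that power is about 76% at N = 74 if the true difference is −0.68 with 15% dropout.

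**Protocol 10.1 and SAP 2.3.** Either put the single-stage and futility-design powers on one stated basis (t or normal), or state how 82.53% was obtained.

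**Leave unchanged.** The promising-zone upper limit and reestimation target remain at 82.53%. They are prespecified and agree with the stated final beta of 0.175; changing them would alter the adaptive rule.

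**Cost.** Text only: no change to N, boundary or analysis. If the optional sentence is added, the synopsis shows a less favourable figure for an effect smaller than the one assumed.
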